### **Exclusion criteria:**

1. Previous myocardial infarction by history or ECG
2. Previous revascularization or valvular heart disease
3. Baseline abnormalities that may obscure electrocardiographic changes during exercise
  - Left bundle branch block or Right bundle branch block
  - Left ventricular hypertrophy with repolarization abnormality
  - Digitalis therapy
  - Ventricular paced rhythm
  - Wolf-Perkinsson-White syndrome
  - ST abnormality associated with supraventricular tachycardia or atrial fibrillation

## **Procedures during study**

### **Exercise Treadmill Testing**

Patients will be undergoing treadmill testing using Bruce treadmill protocol. Before treadmill testing, the patients will be given a questionnaire. This questionnaire will estimate the patient's exercise capacity before the test and thus will allow most patients to reach maximal exercise capacity (Myers 1994). Visual ST-segment deviation will be measured at the J junction and will be corrected for pre-exercise ST-segment depression while standing; ST slope will be measured over the following 80 ms and will be classified as up sloping, horizontal, or down sloping. Slope will be coded as 1 horizontal, down sloping, or upsloping ST depression and 0 for normal slope (up sloping  $<2$  mm or ST-segment depression of  $<0.5$  mm). The ST response will be considered which has the most horizontal, downsloping or up sloping ST-segment depression in any lead, except aVR, during exercise or recovery. An abnormal response will be defined as  $\geq 1$  mm of horizontal or downsloping or  $\geq 2$  mm upsloping ST-segment depression (Griffin 2013). The exercise tests will be analyzed, and reported per standard protocol and manual calculation. Decision for cardiac catheterization will be consistent with clinical practice. Analyses will be performed with the investigators blinded to clinical and angiographic results.

### **Coronary Angiography**

Coronary artery narrowing will be visually estimated and expressed as percent lumen diameter stenosis. Patients with a 70% narrowing in one or more of the following is considered to have significant angiographic coronary artery disease: the left anterior descending, left circumflex, right coronary arteries or their major branches, or a 50% narrowing in the left main coronary artery (Kern 2013).

### **Treadmill Scores**

Treadmill scores and their calculation are shown in Appendix A.

### **Data collection:**

Data will be recorded in pre-designed questionnaires by history, clinical examination and investigation with the patient of University Cardiac Center, BSMMU.

### **Quality assurance strategy:**

A set of questionnaire will be formulated & checked. To make the study credible, reliable & dependable data will be collected by principal investigator by using those questions over a month of period. Again the questions will be edited accordingly & necessarily after discussion with the guide and co-guide of this study.

### **Ethical Issues**

At first ethical clearance will be taken from the ethical review committee of Bangabandhu Sheikh Mujib Medical University (BSMMU). The study will be carried out according to 1964 Helsinki Declaration for Medical Research involving Human subjects and amended by the 64th World Medical Association General Assembly, October 2013. No drugs or placebo will be used for this study. Each participant will enjoy every right to participate or refuse participation. They will be free to withdraw their participation at any stage of the study. Data taken from the participants will be regarded as confidential. Data will be used only for this scientific study. Participants will be informed in detail about the nature and purpose of the study, and informed written consent will be taken from each participant.

## Sample size calculation

Sample size is calculated by using the following equation (One sample comparison of proportion):

$$n = \frac{[Z\beta\sqrt{p(1-p)} + Z\alpha\sqrt{p_1(1-p_1)}]^2}{(p-p_1)^2}$$

n = required sample size

p = Proportion under alternative hypothesis that is proposed to be detected or worst possible outcome

p1= Proportion under null hypothesis or proportion in the population

Z $\alpha$  = 1.96 (5% level of significance)

Z $\beta$  = 1.28 when power is 0.9

According to Fearon WF et al (2002) the predictive accuracy of DTS is 71% (0.71).

If we assume: p1= 0.71

P = 0.55, Power = 0.8,  $\alpha$  = 0.05

$$\begin{aligned} \text{Sample size} &= \frac{[1.28\sqrt{.55(1-.55)} + 1.96\sqrt{.71(1-.71)}]^2}{(.55 - .71)^2} \\ &= 91 \end{aligned}$$

Correction for non-response:

Nf= 100/100- Nr

If Nr= Percentage of expected non-response is 10%

Nf= 100/100- 10 = 1.11

[figure not shown]
Final sample size will be estimated sample size (n) x Nf

= 91 x 1.11 = 102. So our required sample size is at least 102.

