
## Rationale

Though exercise treadmill test has high false positive and negative rates(Zang et al., 2007) , it is cheap, easily available, less time consuming to the interpret results and its accuracy can be increased by calculating ST/HR index, treadmill score, QT dispersion and so on (Kronander 2010 &Dentrano 1989). On the contrary the gold standard test coronary angiogram for detecting CAD is expensive, time consuming, potentially hazardous with many complications and often the CAG shows normal coronary arteries in female population. ST-segment depression and chest pain as the classic criteria for CAD diagnosis are well known and accepted. Besides If treadmill score were used the diagnostic accuracy of ETT would had been higher. The accuracy of different treadmill scores in Bangladeshi population especially the female population is largely unknown. Duke Treadmill Score and Simple Treadmill Score are well validated score in western population and are used for diagnostic & prognostic interpretation of ETT. The predictive accuracy of DTS to diagnose CAD is 71% (Fearon 2002). In 2001 Raxwal V et al. showed simple treadmill score has sensitivity of 88% and specificity of 96%. If we calculate the accuracy of simple treadmill score using the formula “Accuracy = (Sensitivity) x Prevalence + (Specificity) x (1- Prevalence)” it sums up nearly 93% according to prevalence of CAD in urban population. Cleveland Clinic Score is a prognostic score of ETT. It gives value from which we can predict the probability of 3 year or 5 year survival. It was shown that it has a very high negative predictive value approaching 97%. Besides to the best of our knowledge Cleveland Clinic Score was not tested as a diagnostic predictor of CAD and there are few studies regarding treadmill scores predictability in Bangladesh. In our study we will use all of these three scores and compare their accuracy to predict significant CAD. DTS, Simplified Treadmill Score, and Cleveland clinic score can be implemented effectively to identify patients with low probability of CAD and excluded from undergoing expensive and potentially hazardous CAG if the real scenario of the treadmill scores is known in our population.

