## **General Objectives**

To identify difference of predictability of DTS, Simple Treadmill Score and Cleveland Clinic Score to diagnose significant CAD by Coronary Angiography.

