## **Specific Objectives**

1. To estimate accuracy of ST segment response, DTS, Simple Treadmill Score and Cleveland Clinic Score to predict CAD.
2. To compare DTS, Simple treadmill score, Cleveland Clinic Score accuracy to predict coronary artery disease.
3. To identify the relation of different level of treadmill scores with severity of CAD.

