## Statistical Methods

Using angiographic evidence of CAD as the reference, area under the curve (AUC) of receiver operator characteristic (ROC) plots will be determined for the ST response alone and for each treadmill score. The AUC for each treadmill score will be compared with the AUC of the ST response alone and the AUCs of the other treadmill scores. A significant difference is defined as a z-score  $>1.96$ , with  $z\text{-score} = (AUC_1 - AUC_2) / (\text{SE}_1^2 + \text{SE}_2^2)^{1/2}$ . The predictive accuracies of the DTS, the Simple Treadmill Score and Cleveland Clinic Score to stratify patients into high or low likelihood for CAD will be calculated and compared. Test of agreement will be calculated using Kappa statistics. Statistically significant difference between predictive accuracies is defined as a p value  $<0.05$  using the two-tailed Fischer's exact test. Statistical analysis will be performed with the SPSS.

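### The sample size is labelled power 0.8 but computed at 0.9, and it sizes a one-sample DTS test that is not in the analysis plan, so power for comparing the scores is not established

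*Combined protocol and SAP*

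**What the plan says.** The Sample size calculation section names its method: "Sample size is calculated by using the following equation (One sample comparison of proportion". The null value is 0.71, a published predictive accuracy for the DTS. The other value, 0.55, is described as the proportion under the "alternative hypothesis that is proposed to be detected or worst possible outcome". The symbol list defines Z-beta as "1.28 when power is 0.9", and the worked equation uses 1.28. The assumptions line just above that equation says "P = 0.55, Power = 0.8". The result is 91, raised to 102 for 10% non-response, and 102 is then given as the required minimum for the study.

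The general objective is "To identify difference of predictability of DTS, Simple Treadmill Score and Cleveland Clinic Score to diagnose significant CAD". Specific objective 1 is to estimate accuracy. Specific objective 2 is "To compare DTS, Simple treadmill score, Cleveland Clinic Score accuracy to predict coronary artery disease".

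Statistical Methods plans pairwise AUC comparisons by a z-score, kappa, and a comparison of accuracies between scores: "Statistically significant difference between predictive accuracies is defined as a p value" below 0.05 from a two-tailed Fisher's exact test. It contains no test of DTS accuracy against 0.71.

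**The concern.** Two separate things need attention.

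First, one calculation carries two powers, and a reader cannot tell from the section which was intended.

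Second, the calculation answers a question the analysis does not ask. The study exists to compare three scores with each other. The sample size concerns one score against a fixed literature value. The section gives no between-score difference, expected AUC, CAD prevalence among the patients, or correlation or discordance between scores, and at least some of these are needed to power a comparison. Yet it presents 102 as the required size without limiting what that number covers. A reader will naturally attach 0.8 or 0.9 to the main comparison, and may then take a non-significant difference between scores as evidence that they perform alike.

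**Working it through.** **1. Reproducing the plan's figure.** Inputs from the Sample size calculation section: p = 0.55, p1 = 0.71, Z-alpha = 1.96, Z-beta = 1.28, non-response 10%.

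n = [Z-beta·√(p(1−p)) + Z-alpha·√(p1(1−p1))]² / (p − p1)²

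- 1.28 × √(0.55 × 0.45) = 0.6368
- 1.96 × √(0.71 × 0.29) = 0.8894
- n = (0.6368 + 0.8894)² / 0.16² = 90.98, so 91
- 91 / 0.9 = 101.1, so 102

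Both stated figures reproduce. Solving the same formula for power at n = 91 gives 0.900.

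**2. The same formula at the stated power of 0.8** (Z-beta = 0.84).

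- 0.84 × √(0.55 × 0.45) = 0.4179
- n = (0.4179 + 0.8894)² / 0.16² = 66.76, so 67
- 67 / 0.9 = 74.4, so 75

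Only 0.9 yields 91 and 102.

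**3. What n = 91 gives for specific objective 1.** The 95% half-width around an accuracy of 0.71 is 1.96 × √(0.71 × 0.29 / 91) = 0.093, or about ±9 percentage points.

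**4. Illustrative power for comparing two accuracies.** Two-sided exact Fisher test, alpha 0.05, 91 v 91. The scores are treated as independent samples, as that test does.

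| Accuracies compared | Origin of the second value | Power |
|---|---|---|
| 0.71 v 0.93 | Rationale, Simple Treadmill Score: "it sums up nearly 93% according to prevalence of CAD in urban population" | 97% |
| 0.71 v 0.88 | Lowest accuracy compatible with the quoted 88% sensitivity and 96% specificity, since accuracy is a weighted average of the two | 78% |
| 0.71 v 0.55 | The plan's worst-case DTS value, not another score | 56% |
| 0.71 v 0.80 | A consensus score cited in the Introduction, not studied here | 24% |

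With all 102 patients, the last two rows become 61% and 27%. Against 0.71 at 91 v 91, 80% power is reached when the other score is at about 0.885 or higher (power 0.805) or about 0.495 or lower (0.814). That is roughly 17 points upward or 21 downward.

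**5. If a paired test were used instead.** McNemar, 80% power: n = (1.96√ψ + 0.84√(ψ − d²))² / d², where ψ is the proportion of patients on whom two scores disagree in correctness and d is the accuracy difference. The documents do not give ψ, so it is assumed.

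| n | d at ψ = 0.20 | d at ψ = 0.30 | d at ψ = 0.40 |
|---|---|---|---|
| 91 | 0.130 | 0.159 | 0.183 |
| 60 (assumed) | 0.159 | 0.194 | 0.224 |

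The second row is for the case where patients in an intermediate score band (defined in Appendix A) drop out of a low/high comparison. The figure of 60 is an assumption.

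**6. AUC comparison.** The Literature Review gives 0.83 for the DTS. Against an assumed 0.73, with 102 patients and assumed CAD prevalence of 50% to 70%, power is about 0.34 with the plan's z formula. It is about 0.46 to 0.58 if a correlation of 0.3 to 0.5 between the AUC estimates is assumed and taken into account.

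**The case against.** The power label is a small slip in the safe direction: the symbol list, the equation and the result all agree on 0.90, and 102 exceeds the 75 that 0.80 would need. That stands. Alone it would be an editorial correction.

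A one-sample proportion is a usable basis for specific objective 1, and the section never says its power covers comparisons between scores. Both are true, so the calculation should be kept for that purpose. They do not help the general objective or specific objective 2, for which nothing is derived.

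The Fisher illustrations can be challenged. The dummy tables show Fisher only on each score-by-CAD table, which tests association and not one score against another. However, the Statistical Methods text assigns Fisher to differences between accuracies, so the illustration follows the plan's wording. The 91 v 91 setting is also favourable. If intermediate bands left 60 patients per score, power would fall to 86%, 56%, 37% and 15% for the four rows in the order shown, and the ±9 points would become about ±11.5. The 0.93 is itself weak: the plan's formula with the only urban prevalence it quotes, 19.6%, gives 0.88 × 0.196 + 0.96 × 0.804 = 0.944, and general-population prevalence does not describe patients selected for angiography. These points qualify the illustrations, not the finding.

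Finally, a confidence interval for each between-score difference would let a non-significant result be read without any prior power claim. That is fair, and it is compatible with the correction below.

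**Conclusion.** The point holds, and should be fixed. As written, the stated power of 0.8 is wrong for n = 91; the plan's own numbers give 0.90. This does not make the study too small for the test it was sized on.

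That test is not among the planned analyses, and the comparisons that form the general objective have no derived power. Neither 0.8 nor 0.9 applies to them. The illustrative values, from 24% to 97% for accuracy under Fisher, show how strongly the answer depends on a between-score gap the plan does not specify. They rest on assumed true accuracies, on all 91 patients contributing to each score, and on treating the scores as independent. They do not show that the study is underpowered.

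**What to change.** 1. In the assumptions line, change the power from 0.8 to 0.9, to agree with 1.28 and n = 91.
2. Add that 91 (102 with non-response) is sized only for DTS accuracy against 0.71, and that no 80% or 90% power is claimed for comparing scores, whether by AUC or by accuracy. For specific objective 1, the precision may be added: about ±9 points around 0.71 at n = 91, if all 91 contribute.
3. Optional: if a detectable between-score difference is quoted, tie it to the test actually used and state its assumptions. For the Fisher test against 0.71 at 91 v 91 and 80% power, it is about 17 points upward or 21 downward. Only if a paired McNemar test is adopted, it is about 13 to 18 points for assumed discordance of 20% to 40%, or about 16 to 22 points if only an assumed 60 patients contribute.

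The cost is one number and two or three sentences. No extra patients and no added hypothesis test are needed. The price is a less favourable statement: the plan can no longer be read as having a set power for its main question.

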## Statistical Methods

Using angiographic evidence of CAD as the reference, area under the curve (AUC) of receiver operator characteristic (ROC) plots will be determined for the ST response alone and for each treadmill score. The AUC for each treadmill score will be compared with the AUC of the ST response alone and the AUCs of the other treadmill scores. A significant difference is defined as a z-score  $>1.96$ , with  $z\text{-score} = (AUC_1 - AUC_2) / (\text{SE}_1^2 + \text{SE}_2^2)^{1/2}$ . The predictive accuracies of the DTS, the Simple Treadmill Score and Cleveland Clinic Score to stratify patients into high or low likelihood for CAD will be calculated and compared. Test of agreement will be calculated using Kappa statistics. Statistically significant difference between predictive accuracies is defined as a p value  $<0.05$  using the two-tailed Fischer's exact test. Statistical analysis will be performed with the SPSS.

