## Literature Review

According to Islam AKMM and Majumder AAS “Coronary artery disease in Bangladesh: A review published in 2013 the exact prevalence of CAD in Bangladesh is not known. Only a limited number of small-scale epidemiological studies are available. Probably the prevalence of IHD was first reported in 1976, which was 0.33%. More recent data indicates CAD prevalence between 1.85% and 3.4% in rural and 19.6% in an urban sample of working professionals. Despite marked disparity in values, there seems to be a rising prevalence of CAD in Bangladesh.

Gianrossi et al. investigated the diagnostic accuracy of ETT through a meta-analysis including 147 published reports involving 24,074 patients who underwent both coronary angiography and ETT. There was a wide variability in sensitivity and specificity of ETT [sensitivity  $68 \pm 16\%$  (range 23–100%); specificity  $77 \pm 17\%$  (range: 17–100%)]. Another Meta analysis showed sensitivity of  $81 \pm 12\%$  (range: 40–100%) and specificity of  $66 \pm 16\%$  (range: 17–100%).

2014 Taimur et al evaluated ETT (Treadmill) Positive Patients in a Tertiary Care Hospital of Bangladesh by doing angiogram subsequently. They found the overall positive predictive value of ETT is 77.9%, and for male patient PPV is 86.25% and for female patient it is 50%.

In 1987 Mark DB et al showed Duke Treadmill Score was useful for stratifying prognosis in patients with suspected coronary artery disease who were referred for catheterization, and may provide a useful adjunct to clinical decision making in the larger population of patients being evaluated for chest pain. They had evaluated 2842 patients with chest pain who had both treadmill testing and cardiac catheterization.

Shaw LJ et al in 1998 estimated DTS provides accurate diagnostic and prognostic information for the evaluation of symptomatic patients evaluated for clinically suspected ischemic heart disease.

In 2015 Gunaydin et al showed there was a strong negative correlation between DTS and Syntax Score ( $r = -0.72$ ,  $p < 0.001$ ). The area under the receiver-operating curve of DTS was 0.83 (0.77-0.88,  $P < 0.001$ ) for predicting significant presence of CAD. The optimal cut-off value of DTS to predict the significant presence of CAD was -3.7 (sensitivity of

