## **Materials and Methods**

### **Study design**

Type of study: Cross sectional study

As we want to correlate the different treadmills scores and identify which one is better to predict coronary artery disease in male and female population, cross sectional study is good one. By this study design we can find the different treadmill scores and angiographic data within a short time, easily and with less cost.

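### The study is justified by accuracy in men and women, women especially, but the plan reports only pooled results; estimates by sex should be added

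*Combined protocol and SAP*

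**What the plan says.** The Rationale states: "The accuracy of different treadmill scores in Bangladeshi population especially the female population is largely unknown". The Study design section gives the purpose as to "identify which one is better to predict coronary artery disease in male and female population". The Abstract for IRB expects the scores to spare unneeded angiography, above all in women. The Study Area section says that having both sexes is necessary for testing the study hypothesis, but gives no expected proportion.

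The analysis does not follow this through. In the Statistical Methods, "area under the curve (AUC) of receiver operator characteristic (ROC) plots will be determined for the ST response alone and for each treadmill score". AUCs are then compared pairwise, and predictive accuracies are compared "using the two-tailed Fischer's exact test". Sex is not mentioned there, in the Specific Objectives or in the Dummy Tables. The dummy AUC table lists the three scores only, so the ST response has no output row at all. The Simple Treadmill Score has separate point sheets for men and women (Appendix A) but is analysed as one variable.

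Sex is item 2 of the data collection form (Appendix C).

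**The concern.** A reader of the Rationale expects to learn how these tests perform in women. As planned, the study would publish one AUC and one accuracy per score for both sexes together.

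The Literature Review gives reason to expect that the sexes differ in ways that affect such figures. For a Bangladeshi tertiary hospital it reports that "the overall positive predictive value of ETT is 77.9%, and for male patient PPV is 86.25% and for female patient it is 50" per cent. In a cited series of 976 women and 2,249 men, CAD prevalence was 32% against 72% and mean Duke score 1.6 against -0.3.

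Two things can go wrong. A pooled figure can look acceptable while performance in women is clearly worse, or clearly better. And a score whose level differs by sex can gain pooled AUC simply because sex is related to disease, which could affect the ranking of the scores.

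**Working it through.** **The plan's sample size.** With p = 0.55, p1 = 0.71, Zβ = 1.28 and Zα = 1.96, n = [1.28√(0.55×0.45) + 1.96√(0.71×0.29)]² / 0.16² = (0.637 + 0.889)² / 0.0256 = 90.98, i.e. 91. Then 91 × 1.11 = 101.01, taken up to 102. The figures reproduce. They are for both sexes together, and the 0.71 comes from a study that the Introduction describes as men only. (The section has "1.28 when power is 0.9" beside "P = 0.55, Power = 0.8". The arithmetic uses the 90% value. This does not affect the present point.)

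**Share of women.** The documents give none. The only figure that can be derived comes from the Bangladeshi predictive values: (86.25 − 77.9)/(86.25 − 50) = 8.35/36.25 = 23%. This matches 69/80 men and 12/24 women, 81/104 = 77.9%. It describes test-positive patients in another series, so 23% and 50% are both used below as assumptions; 23% of 102 is 23–24 women.

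**Masking.** Assume normally distributed scores with unit SD, AUC 0.80 in men (case mean 1.19 above non-cases) and 0.50 in women. The pooled AUC is the average of the four case/non-case pairings, weighted by their frequency. With 23% women and prevalences 72% and 32%, men supply 0.77×0.72/(0.77×0.72 + 0.23×0.32) = 0.883 of cases and 0.77×0.28/(0.77×0.28 + 0.23×0.68) = 0.580 of non-cases.

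- Women centred midway between male cases and non-cases: 0.512×0.80 + 0.371×0.663 + 0.068×0.663 + 0.049×0.50 = 0.725.
- Women 0.6 SD below male non-cases: 0.512×0.80 + 0.371×0.897 + 0.068×0.336 + 0.049×0.50 = 0.790.

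With assumed prevalences of 86% and 50% the first placement gives 0.71. (Those two figures are the predictive values above, borrowed as a second scenario; they are not reported prevalences.) The range at 23% women is therefore about 0.71–0.79. At 50% women the same steps give 0.655–0.741 with 72%/32% and a low of 0.635 with 86%/50%, so about 0.64–0.74.

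**Effect of score level alone.** Assume a true AUC of 0.75 in both sexes (separation 0.954) and 23% women.

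- Women 0.3 SD lower: 0.512×0.75 + 0.371×0.812 + 0.068×0.678 + 0.049×0.75 = 0.768.
- Women 0.6 SD lower: 0.512×0.75 + 0.371×0.864 + 0.068×0.599 + 0.049×0.75 = 0.782.

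With 86%/50% these become 0.773 and 0.790. The gain is about 0.02–0.04.

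**Precision in women.** The Hanley–McNeil variance at AUC 0.70 is [0.21 + (a−1)×0.0485 + (b−1)×0.0865]/(ab), for a women with CAD and b without.

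- 12 and 12: √(1.694/144) = 0.108, half-width ±0.21.
- 7 and 16 (32% of 23): √(1.798/112) = 0.127, half-width ±0.25.
- 16 and 35 (32% of 51): √(3.877/560) = 0.083, half-width ±0.16.

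**Power of the plan's own test in women alone.** Power is Φ{[0.16√n − 1.96√(0.71×0.29)]/√(0.55×0.45)}: 40% with 23 women and about 70% with 51, against 93% with all 102.

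**The case against.** The research question and the three specific objectives concern the Bangladeshi population as a whole, and none asks for results by sex. That stands as a description of the objectives. It does not answer the Rationale and Study design, which promise more than the objectives deliver.

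A reader might infer from the predictive values of 86.25% and 50% that the test discriminates worse in women. The documents do not support this, because predictive value depends on prevalence. In men, posterior odds of 0.8625/0.1375 = 6.27 over prior odds of 0.72/0.28 = 2.57 give a likelihood ratio of 2.44. Applied to women, 2.44 × 0.32/0.68 = 1.15, a predictive value of 53%, close to the reported 50%. This joins two cited series and is only illustrative, but it shows that the gap is compatible with equal discrimination. The cited ST-based accuracies (70.2% in men, 50.0% in women) do not settle it either: the 70.2% is described as 73 of 104 men positive on both tests, which may be an agreement proportion.

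A reader might also infer that the scores fail in women. The same cited series that supplies the prevalences reports that the Duke score separated prognostic groups equally well in both sexes and did better in women for excluding disease. Finally, a reader might infer that pooled results would speak mainly for men. No sex ratio is stated, and the Study Area section describes the mixture as favourable.

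Two practical objections have weight. With about 23 women, an interval of ±0.21 to ±0.25 cannot separate an AUC of 0.70 from 0.50. And making a within-sex comparison the main analysis would change what is being estimated.

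**Conclusion.** The point holds as a mismatch between the stated purpose and the planned output: the case for the study rests on performance in both sexes, women especially, and no result by sex is planned. Pooling can hide a difference in either direction. The documents do not show that it will, nor that any score fails in women.

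The sizes in the working rest on assumed AUCs, normal scores, an assumed share of women (23% or 50%) and assumed level shifts, since no within-sex SD is given. The level effect of about 0.02–0.04 lies inside the pooled 95% half-width of about 0.08 (for an AUC of 0.83), and it alters the ranking only where it differs between scores. This is a worthwhile, inexpensive improvement; the pooled analysis remains valid for the population-wide question.

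**What to change.** In the Statistical Methods and Dummy Tables:

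- Keep the pooled analysis as the main one.
- Add AUC, sensitivity and specificity with 95% CIs for the ST response, Duke score, Simple Treadmill Score and Cleveland Clinic Score, separately in men and in women, labelled as estimation only. Give the ST response its own row.
- Add a sex-stratified comparison of AUCs between scores as a sensitivity analysis.
- State the expected number of women, and that conclusions about women will rest on the estimates in women and not on the pooled result alone.

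The cost is wording, extra table columns and one additional analysis; no new data item is needed. The drawback is the wide intervals in women, which should be shown as they are.
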